APPENDIX A – SCHEDULE OF ACTIVITIES – STAGE 2, Cycles 2 - 4 (ACM vs CM)

TESTS/PROCEDURES	CYCLES 2+ ^a							End of Study	Follow Up ^v
	At Least 10 Hrs Prior to 1 st Dose	Just Prior to 1 st Dose	Dosing	Daily During Hospitalization for Chemo	Weekly - Post Treatment	At Hematologic Recovery or Day 45 (±2)			
Pretreatment: IV hydration, allopurinol, oral phosphate binder	X ^{k,l,m}								
Monitor urine output frequently ^b	X	X	X	X			X ^p		
ECHO or MUGA	X ⁿ						X ^{r,t}		
Physical examination+weight (kg)		X							
Determination of BSA		X ^o					X		
Vital signs ^c		X					X		
ECOG performance status		X					X		
Hematology ^d		X	X	X	X		X		
Tumor lysis labs ^e		X	X	X	X		X ^p		
Coagulation: fibrinogen		X ^p	X ^p	X ^p	X ^p		X ^p		
Pregnancy test ^f		X							
Concomitant medications ^g		X	X	X	X		X		
Treatment with ACM or CM			X ^q	X ^q	X ^q				
Prophylactic antibiotics and antivirals, steroid eye drops, antifungals			X						
Assessment of AEs ^h			X	X	X		X		
Bone marrow biopsy/ aspirate							X ^{s,u}		
Full serum chemistry panel ⁱ							X		
Urinalysis ^j							X		
12-lead ECG							X ^p		
Telephone call to patient									X

Notes:

a Mitoxantrone must be omitted from subsequent cycles if the patient's lifetime daunorubicin equivalent exceeds 460 mg/m² (see Appendix G for conversion table) or the LVEF drops below 45%. Patients not demonstrating evidence of CR, CRi, CRp, or PR after the first cycle of treatment will be considered for removal from the study, although with permission of the Medical Monitor, induction treatment may continue if clinically indicated and provided there is no evidence of toxicity ≥NCI CTCAE grade 4. However, patients randomized to CM with progressive disease or no response after

- 1 cycle of CM may cross over to receive ACM. In addition, patients randomized to CM with the best response of a PR after 2 cycles of CM may also cross over to receive ACM. Patients who cross over to ACM may receive up to a *combined* total (CM + ACM) of 4 cycles (See [Section 4.5.3.4](#))
- b If pretreatment to manage/treat tumor lysis syndrome is clinically indicated in subsequent cycles, must monitor urine output **frequently** to ensure that it equals fluid input. If input is greater than output by 10%, administration of diuretics is encouraged. Replacement of excessive fluid losses, including from diarrhea, should be done unless otherwise clinically indicated.
- c Vital signs to include: body temperature, heart rate, systolic and diastolic blood pressure
- d See [Appendix D](#) – Laboratory Tests, Hematology
- e See [Appendix D](#) – Laboratory Tests, Tumor Lysis Labs
- f Collect urine or serum sample for β -hCG pregnancy test from females of child-bearing potential
- g To include only those medications (prescription, nonprescription, nutritional supplements) administered in conjunction with an AE.
- h Toxicities will be assessed according to the NCI CTCAE, version 5.0 in Stage 2 (see [Appendix C](#)). When the NCI CTCAE grade is not available, the investigator will use the following toxicity grading: mild, moderate, severe, life-threatening or fatal
- i See [Appendix D](#) – Laboratory Tests, Full Serum Chemistry
- j See [Appendix D](#) – Laboratory Tests, Urinalysis
- k If clinically indicated, begin IV hydration with 0.45% NaCl (or similar hydration fluid per institutional standard) sterile solution at 100 cc/hour at least 10 hours prior to initiation of first dose in both treatment arms.-If, by Day 4, there is no evidence of tumor lysis syndrome, the hydration rate can be reduced to a maintenance level.
- l If clinically indicated, begin allopurinol orally each day of dosing at same time as initiation of IV hydration in both treatment arms.
- m If clinically indicated, begin oral phosphate binder at the same time as initiation of IV hydration in both treatment arms, unless contraindicated.
- n ECHO or MUGA scan to be performed before each dose of mitoxantrone. If mitoxantrone is omitted after Cycle 1, the ECHO or MUGA scan can also be omitted.
- o Measured 5-15 minutes prior to the initiation of infusion following a 5-minute rest
- p Only required if clinically indicated
- q Continued use of mitoxantrone is optional. Mitoxantrone must be omitted from subsequent cycles if the patient's lifetime daunorubicin equivalent exceeds 460 mg/m² (see [Appendix G](#) for conversion table) or the LVEF drops below 45%.
- r Abbreviated physical examination (AE- or symptom-directed exam).
- s Bone marrow biopsies and/or aspirates will be performed at hematologic recovery (ie, absolute neutrophil count (ANC) >1000 μ L and platelet count >100,000 μ L) or on Day 45 (\pm 2), whichever occurs first. If the bone marrow biopsy and/or aspirate is nonproductive or not diagnostic, the procedure must be repeated within 7 days. At time of response assessment and end-of-study visit, 6 to 8 bone marrow slides will be prepared and sent to the Sponsor. Details regarding the collection and shipping of these slides is provided in the Study Manual.
- t Including other measures of disease and disease symptoms, eg, extramedullary disease
- u If not done in preceding 30 days
- v Patients will be contacted by telephone to assess for date of death, date of stem cell transplant, date of relapse, or continued remission for two years: Year 1: Phone calls monthly beginning the month after the patient completes the end-of-study assessments to 12 months after Day of Randomization regardless of how many cycles a patient receives (Year 1 = Day of Randomization plus 12 months); Year 2: Phone calls every other month during Year 2 (months 14 to 24 months after Day of Randomization).

APPENDIX B – ECOG PERFORMANCE STATUS SCALE

ECOG PERFORMANCE STATUS*	
Grade	ECOG
0	Fully active, able to carry on all pre-disease performance without restriction
1	Restricted in physically strenuous activity but ambulatory and able to carry out work of a light or sedentary nature, e.g., light house work, office work
2	Ambulatory and capable of all selfcare but unable to carry out any work activities. Up and about more than 50% of waking hours
3	Capable of only limited selfcare, confined to bed or chair more than 50% of waking hours
4	Completely disabled. Cannot carry on any selfcare. Totally confined to bed or chair
5	Dead

Available at: http://www.ecog.org/general/perf_stat.html

*The ECOG Performance Status is in the public domain therefore available for public use. To duplicate the scale, please cite the reference above and credit the Eastern Cooperative Oncology Group, [name], Group Chair.

APPENDIX C – NCI COMMON TERMINOLOGY CRITERIA FOR ADVERSE EVENTS

View the National Cancer Institute Common Terminology Criteria for Adverse Events (NCI CTCAE) v4.03 (for Stage 1) and v5.0 (for Stage 2) electronically at the following Web sites:

https://evs.nci.nih.gov/ftp1/CTCAE/CTCAE_4.03/CTCAE_4.03_2010-06-14_QuickReference_8.5x11.pdf

https://ctep.cancer.gov/protocoldevelopment/electronic_applications/docs/CTCAE_v5_Quick_Reference_8.5x11.pdf

The Study Manual includes copies of both versions of the NCI CTCAE.

APPENDIX D – LABORATORY TESTS

Hematology	
 CBC with manual differential Platelet Count 
Note: A manual differential is the preferred method and is required on each day that the assessment is done. Automated differentials may be used for subsequent differentials performed on the same day.

Full Serum Chemistry	
 Blood urea nitrogen (BUN) Phosphorus Magnesium Lactate dehydrogenase (LDH) Creatinine Uric acid Total protein Albumin Calcium Glucose Total bilirubin Alkaline phosphatase (ALP) Aspartate aminotransferase (AST) Alanine aminotransferase (ALT) Electrolytes 
 Sodium Potassium Chloride Carbon dioxide (bicarbonate)
Tumor Lysis Labs	
 Phosphorus Uric acid Electrolytes (sodium, potassium, chloride, and carbon dioxide) LDH* Creatinine Calcium
Coagulation	
 Fibrinogen
Urinalysis	
 Color Specific gravity pH Bilirubin Ketones Glucose Occult Blood (Hemoglobin) Leukocyte esterase Protein Urobilinogen Nitrites Microscopic 
 White blood cells (WBCs) Red blood cells (RBCs) Casts, crystals, bacteria
Cardiac Tests	
 12-lead Electrocardiogram (ECG) Echocardiogram (ECHO) or Multigated Acquisition (MUGA) scan
Pharmacodynamic Tests	
 MCL-1 dependence by mitochondrial profiling in bone marrow
Other Tests	
 Pregnancy test (urine or serum determination of β-hCG in females of childbearing potential) Chest radiograph

*Recommended every 24 hours in patients receiving alvocidib.

APPENDIX E – RESPONSE CRITERIA

Response to treatment will be evaluated according to different criteria depending on the stage of the study.

During Stage 1, responses will be defined by the International Working Group and 2010 European LeukemiaNet Criteria.

During Stage 2, responses will be defined by the 2017 European LeukemiaNet Criteria.

INTERNATIONAL WORKING GROUP CRITERIA

Response Criteria in AML

Response Criterion	Time of Assessment	Neutrophils (μL)	Platelets (μL)	Bone Marrow Blasts (%)	Other
Early treatment assessment	7-10 days after therapy	NA	NA	< 5	
Morphologic leukemia-free state	Varies by protocol	NA	NA	< 5	
Morphologic CR	Varies by protocol	> 1,000	> 100,000	< 5	Flow cytometry EMD Transfusion EMD
Cytogenetic CR	Varies by protocol	> 1,000	> 100,000	< 5	Cytogenetics—normal, EMD
Molecular CR	Varies by protocol	> 1,000	> 100,000	< 5	Molecular—negative, EMD
Partial remission	Varies by protocol	> 1,000	> 100,000	> 50 or decrease to 5-25	Blasts < 5% if Auer rod positive

Abbreviations: AML, acute myelogenous leukemia; EMD, extramedullary disease; CR, complete remission.

Definition of Treatment Outcomes

Outcome	Response Category	Point of Measurement	Definition
Overall survival	All patients	Entry onto trial	Death from any cause
Relapse-free survival	CR	Leukemia-free state	Disease relapse or patient death from any cause
Event-free survival	All patients*	Entry onto trial	Treatment failure, disease relapse, or patient death from any cause
Remission duration	CR	Date of CR	Disease relapse

NOTE. Complete blood counts should be evaluated at least monthly, or more often if clinically indicated, to establish the durability of responses.

Abbreviations: AML, acute myelogenous leukemia; CR, complete remission.

*Under circumstances where presentation of event-free survival may be appropriate for responders only, this point should be clearly stated.

Source: Cheson BD, et al. J Clin Oncol 2003;21:4642-4649.

2010 EUROPEAN LEUKEMIANET CRITERIA Response Criteria in AML

Category	Definition
Complete remission (CR)*	Bone marrow blasts < 5%; absence of blasts with Auer rods; absence of extramedullary disease; absolute neutrophil count > $1.0 \times 10^9/L$ (1000/ μL); platelet count > $100 \times 10^9/L$ (100 000/ μL); independence of red cell transfusions
CR with incomplete recovery (CRI)†	All CR criteria except for residual neutropenia (< $1.0 \times 10^9/L$ [1000/ μL]) or thrombocytopenia (< $100 \times 10^9/L$ [100 000/ μL])
Morphologic leukemia-free state‡	Bone marrow blasts < 5%; absence of blasts with Auer rods; absence of extramedullary disease; no hematologic recovery required
Partial remission (PR)	Relevant in the setting of phase 1 and 2 clinical trials only; all hematologic criteria of CR; decrease of bone marrow blast percentage to 5% to 25%; and decrease of pretreatment bone marrow blast percentage by at least 50%
Cytogenetic CR (CRc)§	Reversion to a normal karyotype at the time of morphologic CR (or CRI) in cases with an abnormal karyotype at the time of diagnosis; based on the evaluation of 20 metaphase cells from bone marrow
Molecular CR (CRm)	No standard definition; depends on molecular target
Treatment failure	
Resistant disease (RD)	Failure to achieve CR or CRI (general practice; phase 2/3 trials), or failure to achieve CR, CRI, or PR (phase 1 trials); only includes patients surviving ≥ 7 days following completion of initial treatment, with evidence of persistent leukemia by blood and/or bone marrow examination
Death in aplasia	Deaths occurring ≥ 7 days following completion of initial treatment while cytopenic; with an aplastic or hypoplastic bone marrow obtained within 7 days of death, without evidence of persistent leukemia
Death from indeterminate cause	Deaths occurring before completion of therapy, or < 7 days following its completion; or deaths occurring ≥ 7 days following completion of initial therapy with no blasts in the blood, but no bone marrow examination available
Relapse¶	Bone marrow blasts $\geq 5\%$; or reappearance of blasts in the blood; or development of extramedullary disease

Definitions of response criteria are based primarily on those given by Cheson et al.²

*All criteria need to be fulfilled; marrow evaluation should be based on a count of 200 nucleated cells in an aspirate with spicules; if ambiguous, consider repeat exam after 5 to 7 days; flow cytometric evaluation may help to distinguish between persistent leukemia and regenerating normal marrow; a marrow biopsy should be performed in cases of dry tap, or if no spicules are obtained; no minimum duration of response required.

†The criterion of CRI is of value in protocols using intensified induction or double induction strategies, in which hematologic recovery is not awaited, but intensive therapy will be continued. In such protocols, CR may even not be achieved in the course of the entire treatment plan. In these instances, the overall remission rate should include CR and CRI patients. Some patients may not achieve complete hematologic recovery upon longer observation times.

‡This category may be useful in the clinical development of novel agents within phase 1 clinical trials, in which a transient morphologic leukemia-free state may be achieved at the time of early response assessment.

§Four studies showed that failure to convert to a normal karyotype at the time of CR predicts inferior outcome.¹¹²⁻¹¹⁵

||As an example, in CBF AML low-level PCR-positivity can be detected in patients even in long-term remission. Normalizing to 10^4 copies of *ABL1* in accordance with standardized criteria, transcript levels below 12 to 10 copies appear to be predictive for long-term remission.¹⁰⁸⁻¹¹⁰

¶In cases with low blast percentages (5-10%), a repeat marrow should be performed to confirm relapse. Appearance of new dysplastic changes should be closely monitored for emerging relapse. In a patient who has been recently treated, dysplasia or a transient increase in blasts may reflect a chemotherapy effect and recovery of hematopoiesis. Cytogenetics should be tested to distinguish true relapse from therapy-related MDS/AML.

Source: Döhner H, et al. Blood 2010;115:453-474.

2017 EUROPEAN LEUKEMIANET CRITERIA

Category	Definition	Comment
Response		
CR without minimal residual disease (CR _{MRD-})	If studied pretreatment, CR with negativity for a genetic marker by RT-qPCR, or CR with negativity by MFC	Sensitivities vary by marker tested, and by method used; therefore, test used and sensitivity of the assay should be reported; analyses should be done in experienced laboratories (centralized diagnostics)
Complete remission (CR)	Bone marrow blasts <5%; absence of circulating blasts and blasts with Auer rods; absence of extramedullary disease; ANC $\geq 1.0 \times 10^9/L$ (1000/ μ L); platelet count $\geq 100 \times 10^9/L$ (100 000/ μ L)	MRD ⁺ or unknown
CR with incomplete hematologic recovery (CR _i)	All CR criteria except for residual neutropenia (<1.0 $\times 10^9/L$ [1000/ μ L]) or thrombocytopenia (<100 $\times 10^9/L$ [100 000/ μ L])	
Morphologic leukemia-free state (MLFS)	Bone marrow blasts <5%; absence of blasts with Auer rods; absence of extramedullary disease; no hematologic recovery required	Marrow should not merely be "aplastic"; at least 200 cells should be enumerated or cellularity should be at least 10%
Partial remission (PR)	All hematologic criteria of CR; decrease of bone marrow blast percentage to 5% to 25%; and decrease of pretreatment bone marrow blast percentage by at least 50%	Especially important in the context of phase 1-2 clinical trials
Treatment failure		
Primary refractory disease	No CR or CR _i after 2 courses of intensive induction treatment; excluding patients with death in aplasia or death due to indeterminate cause	Regimens containing higher doses of cytarabine (see Table 8) are generally considered as the best option for patients not responding to a first cycle of 7+3; the likelihood of responding to such regimens is lower after failure of a first
Death in aplasia	Deaths occurring ≥ 7 d following completion of initial treatment while cytopenic; with an aplastic or hypoplastic bone marrow obtained within 7 d of death, without evidence of persistent leukemia	
Death from indeterminate cause	Deaths occurring before completion of therapy, or <7 d following its completion; or deaths occurring ≥ 7 d following completion of initial therapy with no blasts in the blood, but no bone marrow examination available	
Response criteria for clinical trials only		
Stable disease	Absence of CR _{MRD-} , CR, CR _i , PR, MLFS; and criteria for PD not met	Period of stable disease should last at least 3 mo
Progressive disease (PD)*, †	Evidence for an increase in bone marrow blast percentage and/or increase of absolute blast counts in the blood: 
 • >50% increase in marrow blasts over baseline (a minimum 15% point increase is required in cases with <30% blasts at baseline; or persistent marrow blast percentage of >70% over at least 3 mo; without at least a 100% improvement in ANC to an absolute level (>0.5 $\times 10^9/L$ [500/μL], and/or platelet count to >50 $\times 10^9/L$ [50 000/μL] nontransfused); or • >50% increase in peripheral blasts (WBC \times % blasts) to >25 $\times 10^9/L$ (>25 000/μL) (in the absence of differentiation syndrome)†; or • New extramedullary disease 	Category mainly applies for older patient given low-intensity or single-agent "targeted therapies" in clinical trials In general, at least 2 cycles of a novel agent should be administered Some protocols may require blast increase in 2 consecutive marrow assessments at least 4 wk apart; the date of progression should then be defined as of the first observation date Some protocols may allow transient addition of hydroxyurea to lower blast counts "Progressive disease" is usually accompanied by a decline in ANC and platelets and increased transfusion requirement and decline in performance status or increase in symptoms
Relapse		
Hematologic relapse (after CR _{MRD-} , CR, CR _i)	Bone marrow blasts $\geq 5\%$; or reappearance of blasts in the blood; or development of extramedullary disease	
Molecular relapse (after CR _{MRD-})	If studied pretreatment, reoccurrence of MRD as assessed by RT-qPCR or by MFC	Test applied, sensitivity of the assay, and cutoff values used must be reported; analyses should be done in experienced laboratories (centralized diagnostics)

ANC, absolute neutrophil count; IDH, isocitrate dehydrogenase; MLFS, morphologic leukemia-free state; WBC, white blood cell.

*The authors acknowledge that this new provisional category is arbitrarily defined; the category aims at harmonizing the various definitions used in different clinical trials.

†Certain targeted therapies, for example, those inhibiting mutant IDH proteins, may cause a differentiation syndrome; that is, a transient increase in the percentage of bone marrow blasts and an absolute increase in blood blasts; in the setting of therapy with such compounds, an increase in blasts may not necessarily indicate PD.

Source: Döhner H, Estey EH, Grimwade D, et al. Blood 2017;129(4):424–447.

APPENDIX F – MULTIVARIATE ANALYSIS AND RISK SCORE PREDICTION MODEL FOR DEVELOPMENT OF TUMOR LYSIS SYNDROME IN AML

Co-variate	Unfavorable categories	Regression coefficient	CTLS Odds ratio (95% CI)	p value	Score*
WBC	≤25×10 ³ /L	1.1	1	<0.001	0
	25-75×10 ³ /L		2.7 (1.4-5.4)		1
	>75×10 ³ /L		7.3 (2.0-29.1)		2
Uric acid	≤7.5 mg/dL	2.2	1	<0.001	0
	>7.5 mg/dL		9.1 (3.3-26.6)		1
LDH	≤1×ULN	1.2	1	0.005	0
	1-4×ULN		3.9 (1.5-10.8)		1
	>4×ULN		15.2 (2.2-96.8)		2

CTLS = clinical tumor lysis syndrome; LDH = lactate dehydrogenase; ULN = upper limit of normal; WBC = white blood cells

*Patients with an overall score of ≥2 will be considered at high risk for development of TLS in this study.

Source: Montesinos P, Lorenzo I, Martín G, et al. Haematologica 2008;93(1):67–74.

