	
recovery (absolute neutrophil count [ANC] >1000 μL and platelet count >100,000 μL); independence of red cell transfusions (In Stage 2, per 2017 ELN, independence of red cell transfusions is not a requirement for CR); plus
 
 ○ CRi = Meets all CR criteria except for residual neutropenia (ANC <1000 μL) or lack of recovery of any other hematopoietic cell; plus ○ CRp = Meets all CR criteria except for residual thrombocytopenia (platelet count <100,000 μL) † 
 ● Combined Response Rate = Percentage of patients achieving: 
 ○ CR ○ CRi ○ CRp † ○ PR = Meets all hematologic values required for CR but with a decrease of at least 50% in the percentage of blasts to \geq5% to \leq25% in bone marrow ● Overall Survival (OS) = Time from randomization (Day 1) until death from any cause ● Event-free Survival (EFS) = Time from randomization (Day 1) until (a) treatment failure, (b) relapse after CR, or (c) death from any cause, whichever occurs first, censored at 2 years ● Rate of Stem Cell Transplantation = Percentage of patients proceeding directly to stem cell transplantation 
†Note that CRp has been retained in definitions for Combined CR Rate and Combined Remission Rate because Stage-1 patients were assessed using the IWG criteria. CRp will not be used for assessing response in Stage-2 patients and, therefore, will not be included in the definitions of Combined CR Rate and Combined Remission Rate in Stage 2.
 
The CR rate in patients failing 1-2 cycles of CM and crossing over to receive ACM will also be determined.
 
The Complete Remission (CR) rate, defined as the percentage of patients achieving CR, will be determined. Secondary endpoints described for Stage 1 will also be assessed.
 
Complete details of the planned analysis will be documented in a full Statistical Analysis Plan, which will be finalized before locking the study database.

Safety Evaluations:
	
Safety and tolerability of the ACM and CM regimens will be assessed by analyzing the incidence rates of treatment-emergent adverse events summarized within treatment groups at the MedDRA preferred term and primary system organ class levels. Similar summaries will be made for subsets of AEs such as (1) those judged by the Investigator to be related to study treatment, and (2) serious adverse events (SAEs). The multivariate analysis and risk score prediction

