11.3 Analysis Populations

- **Intent-to-treat (ITT) patient population:** includes all patients enrolled into Stage 1; the exploratory arms; or randomized to receive study drug in Stage 2 regardless of whether they actually received study drug and regardless of whether evidence is found indicating they failed to meet study inclusion/exclusion criteria or had other protocol violations. When the ITT patient population is analyzed, Stage 2 patients are grouped according to their randomized treatment regardless of actual treatment received. The ITT patient population is the analysis population for all primary statistical inference and tests of hypotheses related to efficacy endpoints.
- **Safety patient population:** a subset of ITT patients who received at least one dose of study drug. When the safety patient population is analyzed, patients are grouped according to actual treatment received. ACM is considered a patient's "treatment received" in the safety patient population if alvocidib is administered at any time during the study. The safety patient population is the analysis population for all analyses of safety data.
- **Per-protocol patient population:** a subset of the safety patient population who either (a) have at least one response evaluation on study, or (b) die prior to their first scheduled response evaluation. However, patients are excluded from the per-protocol patient population if they have

an important protocol deviation, such as when evidence is found indicating they failed to meet any study inclusion/exclusion criterion. When the per-protocol patient population is analyzed, patients are grouped according to actual treatment received. ACM is considered a patient's "treatment received" in the per-protocol patient population if alvocidib is administered at any time prior to CR (or at any time during the study for patients never achieving CR). The per-protocol population is used for sensitivity (secondary, supportive) analyses of efficacy endpoints.

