- **Response-assessment population:** a subset of the safety population who have at least one response evaluation on study. When the response-assessment patient population is analyzed, patients are grouped according to actual treatment received. ACM is considered a patient's "treatment received" in the response assessment patient population if alvocidib is administered at any time prior to CR (or at any time during the study for patients never achieving CR). The response-assessment population is the primary population for assessing the correlation between MCL-1 dependency and response to ACM and is used for sensitivity (secondary, supportive) analyses of efficacy endpoints.

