11.4 Data Analyses

The overall significance level for this study will be 2.5% using one-sided hypothesis tests. Results from Stage 1 will be reported using descriptive statistics and confidence intervals. Primary statistical comparisons of efficacy results will use only data from Stage 2; however, data from Stage 1 patients will be combined with data from patients receiving ACM in Stage 2 for secondary efficacy analyses. Details of the analyses planned for this study are provided in the Statistical Analysis Plan under separate cover.

Stage 2 complete remission (CR) rates will be compared across treatment groups using the Cochran-Mantel-Haenszel general association test stratified by response to most recent induction therapy (refractory [persistent disease or CR duration <90 days], early relapse [CR duration 90 days to 1 calendar year], or late relapse [CR duration >1 calendar year but <24 months]). The same test will be applied to assess statistical significance of secondary response rate endpoints. Control of the overall 2.5% type-1 error rate for multiple comparisons will be achieved using the hierarchical closed test procedure.

Treatment-group distributions of time-to-event endpoints will be compared using the log-rank test stratified by response to most recent induction therapy.

Incidence rates of TEAEs will be summarized within treatment group at the MedDRA preferred term and primary system organ class levels. Similar summaries will be made for subsets of AEs such as (1) those judged by the Investigator to be related to study treatment, and (2) SAEs.

Other routine safety assessments (eg, clinical laboratory parameters and vital signs) will be summarized by treatment group using mean, standard deviation, median, minimum and maximum changes from baseline values.

A DSMB will monitor key outcomes from the study.

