7.10. Biomarker

The biomarker in this study is MCL-1 dependence measured by mitochondrial sensitivity to NOXA BH3 peptides. Relevant data supporting analyses of MCL-1 dependence will be listed by patient within treatment arm. Summary of baseline biomarker values will include within– and between–treatment-arm descriptive statistics appropriate for continuous variables (see section 7.7). An LR model will be fit to examine the relationship between baseline MCL-1 dependence and the independent binary variable cycle-1 CR for relapsed and refractory AML patients receiving ACM. In addition, area under the curve (AUC) will be calculated (by treatment arm) for the trapezoidal receiver operating characteristic (ROC) curve. This value will quantify the ability of MCL-1 dependence to predict cycle-1 CR.¹¹ Ninety-five percent CIs will be calculated by assuming estimated AUC follows a normal distribution.

$$\widehat{AUC} \pm z_{1-\alpha/2} SE_{AUC}$$

where the standard error SE_{AUC} is calculated by the jackknife method.¹² Data from relapsed/refractory patients receiving CM in cycle 1 and patients with newly diagnosed, high-risk AML will not be used in these analyses. Similar analyses will be conducted for (1) cycle-1 combined CR and (2) cycle-1 combined remission.

Quantifying the effect of MCL-1 dependence on response rates will not infer a safety and/or efficacy benefit (or detriment) of treatment with ACM over CM. Therefore, no statistical analyses of MCL-1 dependence across treatment arms are planned other than comparing baseline values to confirm randomization created homogeneous groups with respect to prestudy values.

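### CR is graded by different rules in Stage 1 and Stage 2, and by unstated rules in the exploratory arms, yet the pooled ACM analyses and the MCL-1 model treat it as one outcome

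*Protocol*

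**What the plan says.** Appendix E of the protocol sets the grading rules by stage: "During Stage 1, responses will be defined by the International Working Group and 2010 European LeukemiaNet Criteria", and "During Stage 2, responses will be defined by the 2017 European LeukemiaNet Criteria". Neither document says which rules graded the exploratory arms.

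The Study Summary (Efficacy Evaluations) acknowledges one consequence: "In Stage 2, per 2017 ELN, independence of red cell transfusions is not a requirement for CR". Protocol 4.1 lists transfusion independence as part of CR without that Stage 2 exception. The only other cross-stage note concerns CRp in the combined endpoints. It gives no rule for analysing CR across stages.

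Three provisions then bring differently graded patients together:

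- Protocol 11.4: "data from Stage 1 patients will be combined with data from patients receiving ACM in Stage 2 for secondary efficacy analyses".
- Protocol 11.3: "The response-assessment population is the primary population for assessing the correlation between MCL-1 dependency and response to ACM". That population is a subset of the safety set, which is a subset of an ITT set that "includes all patients enrolled into Stage 1; the exploratory arms; or randomized to receive study drug in Stage 2". The logistic model in 11.4.3 has terms for MCL-1, treatment arm and their interaction, and none for stage or criteria.
- SAP 7.10 models the "relationship between baseline MCL-1 dependence and the independent binary variable cycle-1 CR for relapsed and refractory AML patients receiving ACM". It leaves out only patients given CM in cycle 1 and newly diagnosed patients, so the relapsed/refractory exploratory arms and Stage 1 are in.

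SAP 7.9.1 says that central and local readers both use the protocol's criteria. Central review therefore does not, as written, put CR on one scale.

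**The concern.** The same patient could be a CR in one part of the study and not in another. In a pooled ACM rate, that makes the figure a mixture of two endpoints.

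For the MCL-1 analysis there is a further difficulty, because study part is tied to MCL-1 range. Patients below 30% come only from the exploratory arms (SAP Synopsis). The range from 30% up draws on an exploratory arm, Stage 1 and Stage 2. Part of any fitted slope or AUC could then reflect the rule used to call CR instead of biology. The 95% CI planned for the AUC covers sampling error, not a change of outcome definition.

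Modelling MCL-1 against response to ACM is the third statistical objective in SAP 4.2. Comparisons across MCL-1 bands also feed design decisions: protocol 2.7 cites response of 62% against 52% in two bands when justifying the 30% cutoff.

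**Working it through.** **1. The plan's own figure (context only; it is not disputed).** Inputs from protocol 11.2.2: CR 70% v 30%, one-sided 2.5%, 90% power, 1:1. With unpooled variance, n per arm = (1.960 + 1.282)² × (0.7×0.3 + 0.3×0.7) / 0.4² = 27.6, so 28 per arm and 56 in total, with power 90.4% at 28. This matches. Both randomised arms are graded by 2017 ELN, so neither the sample size nor the primary test is touched.

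**2. The two CR rows in Appendix E.**

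| Component | 2010 ELN (Stage 1) | 2017 ELN (Stage 2) | Effect of moving to 2017 |
|---|---|---|---|
| Red-cell transfusion independence | Required | Not required | Loosens CR |
| Circulating blasts | Not listed | "absence of circulating blasts and blasts with Auer rods" | Tightens CR |
| ANC and platelet thresholds | > | ≥ | Loosens, trivially |

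Marrow blasts below 5%, no Auer rods and no extramedullary disease are common to both. The net direction cannot be read from the text.

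**3. Share of the pooled ACM set under the older rules.** Stage 1 has 23 evaluable patients (protocol 11.2.1) or 25 (protocol 4.4.1), and Stage 2 ACM has 28.

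- 23/(23+28) = 23/51 = 45%
- 25/(25+28) = 25/53 = 47%

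If the two rule sets differ by a net d points, the pooled CR rate differs from an all-2017 rate by share × d. For d = 5 that is 0.472 × 5 = 2.4 points, and for d = 15 it is 7.1 points.

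**4. Effect on the MCL-1 AUC.** The documents give no reclassification rate, so this is an illustration. Assumptions:

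- True CR is 50% at every MCL-1 level.
- There are 14 patients in each of three relapsed/refractory exploratory arms (56/4), with scores uniform within 0-15, 15-30 and 30-40%.
- There are 25 Stage 1 patients, uniform on 40-80%, and 28 Stage 2 ACM patients, uniform on 30-80%.
- d is the CR rate under 2017 ELN minus the rate under the older rules, and there are 3,000 replicates per setting.

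| d (points) | Mean AUC, exploratory arms on older rules | Mean AUC, exploratory arms on 2017 ELN |
|---|---|---|
| −15 | 0.469 | 0.541 |
| −10 | 0.477 | 0.527 |
| −5 | 0.488 | 0.513 |
| 0 | 0.500 | 0.499 |
| +5 | 0.511 | 0.486 |
| +10 | 0.522 | 0.473 |
| +15 | 0.531 | 0.459 |

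The spurious CR gap (30% or above minus below 30%) at d = +15 can be checked by hand. The upper range holds 14 + 25 + 28 = 67 patients. If the exploratory arms used the older rules, 28/67 of these are on 2017 ELN, so the gap is 0.418 × 15 = +6.3 points. If they used 2017 ELN, 25/67 are on the older rules, so the gap is −0.373 × 15 = −5.6 points.

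For scale, with 95 patients split evenly between CR and no CR, the null SE of the AUC is √[96/(12 × 47.5²)] ≈ 0.06. The largest shift is therefore smaller than one SE.

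**The case against.** **The primary result is safe and the pooled work is not confirmatory.** This stands for the primary test. SAP section 7 keeps Stage 1 and exploratory data out of statistical inference. But that passage concerns the first two objectives; the MCL-1 model is the third, and it will be reported with an AUC and interval.

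**The transfusion example may dissolve.** A reader might infer that a Stage 1 patient with a clear marrow and recovered counts, but still transfused, is neither CR nor CRi. The Appendix E rows alone read that way. However, the Abbreviations, Study Summary and protocol 4.1 widen CRi to failed recovery of any other blood cell line, which could cover red cells. SAP section 3 and 7.9.1 then upgrade a first CRi to cycle-1 CR once neutrophils and platelets recover, with no transfusion condition. On that reading the patient counts as a cycle-1 CR after all. The documents do not settle which reading applies, so the stronger claim is not supported. The circulating-blast difference remains either way.

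**The tie to MCL-1 range is an inference.** This is correct, because the exploratory-arm criteria are not stated. The link follows only if those arms used a single rule set, and its sign reverses according to which one. A claim that the AUC is inflated, or deflated, has no support.

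**A biased ACM-versus-CM contrast might be inferred.** Protocol 11.4 does not say that the pooled ACM data will be compared with CM, and it limits primary comparisons to Stage 2.

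**Conclusion.** The point holds in a limited form. Two CR definitions are explicit, patients graded under them are combined, and neither document regrades them or adjusts for the difference. Between 45% and 47% of the pooled Stage 1 plus Stage 2 ACM set carries the older definition. If the exploratory arms used one rule set throughout, MCL-1 below 30% has one definition while 30% and above mixes two.

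The direction is unknown. The size is probably modest: AUC about 0.46-0.54 where the truth is 0.50. This rests on assumed net shifts of up to 15 points, equal exploratory arms and uniform scores, none of which the documents supply. The randomised Stage 2 comparison is unaffected. The change is worth making because it is cheap and removes an artefact from a stated objective, but the trial does not depend on it.

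**What to change.** 1. State in Appendix E which criteria graded the exploratory arms, and reconcile protocol 4.1 with the Study Summary on transfusion independence in Stage 2.
2. Add to protocol 11.4 and 11.4.3 and to SAP 7.10 that every analysis combining study parts classifies all patients by the 2017 ELN rows.
3. Keep the central-review grading as the source and change only the components on which the rules differ: transfusion independence, circulating blasts, and > versus ≥ thresholds. The inputs are the marrow blasts, differential and counts already recorded, plus the Auer-rod and extramedullary findings behind the original grading.
4. Report a Stage 2-only sensitivity analysis.
5. Keep the original grading for the stand-alone Stage 1 report and the decision to proceed.

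Regrading forward to 2017 ELN is the practical direction because it needs no transfusion data. Under protocol 4.7.2, therapies after the first dose are recorded only when given for an adverse event, so grading Stage 2 back to 2010 ELN may not be possible. A stage or criteria term in the model is a weaker substitute, because study part and MCL-1 range are tied together.

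The cost is some wording and a derivation program. The downside is that some patients will carry two responses, which the report must label.
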